1.0 OBJECTIVES

- 1.1 Primary Objective
 - 1.1.1 To measure response rates to anti-emetic therapy (no emetic or retching episodes and no rescue medication use) in the late onset phase (days 4-7) of Granisetron (Sancuso) administered via a transdermal patch compared to orally administered Ondansetron in women with cervical, endometrial or vaginal cancer undergoing chemoradiation therapy.
- 1.2 Secondary Objectives
 - 1.2.1 To measure response rates to anti-emetic therapy (no emetic or retching episodes and no rescue medication use) in the acute (0-24 hours) phase of Granisetron administered via a transdermal patch compared to orally administered Ondansetron in women with cervical, endometrial or vaginal cancer undergoing chemoradiation therapy.
 - 1.2.2 To measure response rates to anti-emetic therapy (no emetic or retching episodes and no rescue medication use) in the delayed (24-72 hours) phase of Granisetron administered via a transdermal patch compared to orally administered Ondansetron in women with cervical, endometrial or vaginal cancer undergoing chemoradiation therapy.
 - 1.2.3 To measure compliance with Granisetron administered via a transdermal patch compared to orally administered Ondansetron in women with cervical endometrial or vaginal cancer undergoing chemoradiation therapy.
 - 1.2.4 To measure amount and effect of nausea/vomiting on quality of life with Granisetron administered via a transdermal patch compared to orally administered Ondansetron in women with cervical endometrial or vaginal cancer undergoing chemoradiation therapy.
 - 1.2.5 To determine if Granisetron administered via a transdermal patch compared to orally administered ondansetron results in less dose reductions of cisplatin in women with cervical, endometrial or vaginal cancer undergoing chemoradiation therapy.
 - 1.2.6 To measure amount of "rescue medication" for chemotherapy-induced nausea and vomiting (CINV) during chemoradiotherapy in women with cervical, endometrial or vaginal cancer undergoing chemoradiation therapy taking Granisetron administered via a transdermal patch compared to orally administered Ondansetron.
- 1.3 Exploratory Objective
 - 1.3.1 Women undergoing definitive chemoradiation therapy for cervical, endometrial or vaginal cancer typically have significant diarrhea as a therapeutic complication. However, 5HT3 blockers tend to cause constipation as a medication side effect. Therefore, we hypothesize that women undergoing chemoradiation therapy and receiving the continuous administration of a 5HT3 blocker via the patch (Sancuso) will have less diarrhea than those receiving only 72 hours of scheduled oral 5HT3 blockers (ondansetron)

2.0 BACKGROUND AND RATIONALE

Worldwide, there will be over 500,000 new cases of cervical cancer diagnosed this year which makes *cervical cancer the second most common cause of cancer death among women*. Multiple phase III trials have shown that platinum-based chemotherapy given with radiation therapy in the treatment of cervical cancer improves disease-free and overall survival when compared with radiotherapy alone (1-3). As a result of these studies, the National Cancer Institute (NCI) in 1999 issued a clinical alert changing the standard-of-care from radiotherapy alone to radiotherapy with concurrent platinum based chemotherapy

in the treatment of locally advanced cervical cancer (4). Based on these data showing improved survival for patients with cervical cancer receiving concurrent cisplatin with pelvic radiation, most providers have begun adding cisplatin to pelvic radiation for patients with vaginal cancer. At MD Anderson, we frequently prescribe concurrent cisplatin with pelvic radiation for women with vaginal cancer as part of our standard of care. In these women with vaginal cancer receiving chemoradiation, the cisplatin dosage and schedule as well as the radiation treatment plan are the same as in women with cervical cancer. In addition to chemoradiation therapy as primary or adjuvant therapy for patients with cervical and vaginal cancers, combination cisplatin and pelvic radiotherapy are commonly used in the adjuvant setting for intermediate and high risk patients with endometrial cancer after hysterectomy and staging. In these women with endometrial cancer receiving adjuvant chemoradiation, the cisplatin dosage and schedule as well as the radiation treatment plan are also the same as in women with cervical and vaginal cancers.

Unfortunately, cisplatin, the agent most commonly administered with radiation therapy, is a well-known emetogenic agent. In a recent phase II study of cisplatin with radiotherapy in women with cervical or endometrial cancer, 100% reported symptoms of nausea with over two-thirds experiencing grade 2 or 3 toxicity (5). The National Comprehensive Cancer Network (NCCN) lists cisplatin among the “highly emetogenic agents” causing chemotherapy induced nausea and vomiting (CINV) in over 90% of patients who do not receive antiemetic therapy after drug infusion. The current recommendations from the NCCN for women receiving cisplatin is to start an anti-emetic therapy prior to starting chemotherapy and to continue for at least 72 hours after administration of infusion as the risk of emesis and nausea for persons receiving cisplatin lasts for at least 4 days.

At MD Anderson Cancer Center and Lyndon B. Johnson General Hospital (LBJ), we typically prescribe oral antiemetic therapy with a 5HT₃ blocker to start with chemotherapy and continue the medication on a scheduled “around the clock” regimen for three days after chemotherapy administration (institutional standard of care). However, up to 27.5% of women receiving chemotherapy will report nausea or emesis on the fourth day after chemotherapy and another 16.5% will report these symptoms on the fifth day after administration (6) (late onset nausea/vomiting) when scheduled anti-emetic therapy has been discontinued. In addition, women receiving cisplatin as part of their treatment for cervical, endometrial or vaginal cancer do so every 7 days which means they are scheduled to take antiemetic treatment for 3 days out of every week. This frequent self-administration of anti-emetic medications only adds to the treatment burden these women are undergoing.

Recently, a new formulation of granisetron in extended release patch (Sancuso) has been shown to be equivalent to scheduled oral administration of ondansetron (Zofran). Instead of thrice daily oral administration of this 5HT₃ blocker, Sancuso provides nausea relief with a single patch that is changed every 7 days. The week long duration of the patch is appealing in its potential to reduce late onset nausea and vomiting in women receiving cisplatin with concurrent radiation. We hypothesize that women receiving weekly cisplatin with pelvic radiation therapy as definitive treatment for cervical, endometrial or vaginal cancer will have less late onset nausea and vomiting (days 4-7) when given Sancuso when compared to oral ondansetron (Zofran) administration. In addition, we believe that patients will have much higher compliance and satisfaction with the once weekly patch formulation of ondansetron when compared with the thrice daily oral administration.

Two studies have evaluated transdermal vs oral granisetron. The first was a randomized phase II study of 210 patients with cancer undergoing moderately emetogenic chemotherapy. There was no difference in total and complete control of nausea, severity of nausea and vomiting or number of emetic episodes in the acute setting (<72 hours after chemotherapy). The most common side effect was headache (3.4% in granisetron patch group, 4.7% in oral granisetron group) and only 1 patient in the granisetron patch group had the patch fall off. The second study was a phase III randomized control study of oral vs. transdermal granisetron in 641 patients undergoing moderately or highly emetogenic chemotherapy. There was no difference between the two groups in the control of nausea and vomiting in the acute phase (i.e. <72

hours after chemotherapy). Constipation was the more common side effect in the patch group (6.6% of patients compared to 3.1% in the oral group).

Chemoradiotherapy with concurrent cisplatin as treatment for cervical or endometrial cancer is an ideal model for a phase III trial of an extended release delivery system of anti-emetic therapy (i.e. Sancuso patch) for the following reasons:

1. CINV from cisplatin is severe and lasts up to 7 days after chemotherapy administration.
2. Cisplatin is administered on a weekly basis making 72 hours of scheduled oral antiemetic therapy 3 days out of every week burdensome.
3. Cisplatin with external beam radiation therapy is only given for 5 weeks establishing a definitive endpoint to rotate subjects off protocol.
4. Cervical cancer is a disease that effects women, and female gender increases risk of CINV (7). In addition, the median age at diagnosis is younger than for most other cancers. Young age is also a risk factor for increased CINV (7).
5. Cervical cancer typically affects women of low socioeconomic status and poor education where understanding and compliance with scheduled anti-emetic drug regimens may be an issue, which could adversely impact delivery of curative therapy.

3.0 PATIENT ELIGIBILITY

3.1 Inclusion Criteria

- 3.1.1 Women with cervical, endometrial or vaginal cancer dispositioned to receive primary or postoperative adjuvant pelvic radiation therapy with concurrent cisplatin administration.
- 3.1.2 Women must be at least 18 years of age.
- 3.1.3 Women must be able to read English or Spanish at a sixth grade level.
- 3.1.4 Women with childbearing potential must have a negative pregnancy test within 1 week of starting chemoradiation therapy.

3.2 Exclusion Criteria

- 3.2.1 Women with cervical endometrial, vaginal cancer who are receiving chemotherapy and/or radiation therapy for recurrent disease.
- 3.2.2 Women with cervical, endometrial or vaginal cancer who are receiving extended field radiation therapy
- 3.2.3 Women with cervical, endometrial or vaginal cancer who are receiving chemotherapy and/or radiation therapy in a palliative setting.
- 3.2.4 Women with cervical, endometrial or vaginal cancer who have already received their first dose of chemotherapy or have received more than 7 days of radiation

4.0 THERAPEUTIC PROGRAM

This phase III study will randomize eligible patients with cervical, endometrial or vaginal cancer undergoing chemoradiation therapy (see above for eligibility criteria) to receive either 34.3 mg of granisetron formulated in a transdermal patch (Sancuso) replaced every 7 days (Group A) **OR** 8 mg of ondansetron orally thrice daily starting with cisplatin administration and continued for 72 hours after chemotherapy infusion (Group B). Patients may not be enrolled on study if they have already started their chemotherapy treatment or have received more than 7 days of radiation prior to starting their chemotherapy.

In addition, data on compliance/ease of administration, amount of nausea and vomiting, and effect of nausea and vomiting on quality of life will also be collected. These data will be collected weekly via self-administered questionnaires that are estimated to take < 5 minutes to complete.

Study Drug and Dosage Schedule

Group A: 34.3 mg of granisetron formulated in a transdermal patch (Sancuso) replaced every 7 days. Patients will have the transdermal patch placed/replaced prior to the IV infusion of cisplatin. At cycle 1, patients will receive IV ondansetron 8mg prior to IV cisplatin. Administration of transdermal patch will be at the start of IV cisplatin. For subsequent cycles, replacement of transdermal patch will start during the premedication period of IV cisplatin.

Group B: 8 mg of ondansetron orally thrice daily starting within 8 hrs of cisplatin administration and continued for 72 hours after chemotherapy infusion.

Cisplatin and premedications will be given per standard order sets and physician discretion.

4.1 Evaluation During Study

All treatments will occur within one week time frame +/- 3 days to allow for scheduling. The patient will be given pill diaries for transdermal patch and/or Ondansetron, rescue medications, and anti-diarrheal medications. Adverse event monitoring and concomitant medications will be recorded prior to each cycle and one week after the last cycle. QOLs will be completed prior to each cycle and one week after the last cycle. Lab work and chemoradiation will be ordered at the discretion of the treating physician.

4.2 Duration of treatment

Treatment will last 5 cycles or until the patient withdraws (Section 8.0), whichever comes first. The patient may continue to receive further chemoradiation after 5 cycles at the discretion of the treating physician; however, the patient will be taken off treatment after 5 cycles.

The transdermal patch and Ondansetron should be continued as scheduled even if the IV Cisplatin is held.

4.3 Study Endpoints

Primary Endpoint:

1. The proportion of patients with a complete response (CR; defined as no emetic or retching episodes and no rescue medication use) during the late onset phase (4-7 days post-chemotherapy) measured during cycle 1 of chemoradiation therapy.

Secondary Endpoints:

1. The proportion of patients with a complete response (CR; defined as no emetic or retching episodes and no rescue medication use) during the acute phase (0–24 h post-chemotherapy) measured during each cycle of chemoradiation therapy.
2. The proportion of patients with a complete response (CR; defined as no emetic or retching episodes and no rescue medication use) during the delayed phase (24–72 h post-chemotherapy) measured during each cycle of chemoradiation therapy.
3. Ease of administration/compliance of two medications measured during each cycle of chemoradiation therapy.
4. Effect of nausea/vomiting on quality of life (Osoba Module – Appendix D) measured prior to each cycle of chemoradiation therapy and one week after the last cycle. Amount of nausea/vomiting in the prior week (Morrow Assessment of Nausea and Emesis (MANE Scale) – Appendix C) measured prior each cycle of chemoradiation therapy and one week after the last cycle
5. The number of dose reductions/patient during the 5 week treatment measured prior to each cycle of chemoradiation therapy.

6. The amount of “rescue medications” utilized during the 5 week treatment, including 1 week after the last cycle of cisplatin, measured during each cycle of chemoradiation therapy.

Exploratory Endpoint:

1. The amount of diarrhea experienced weekly by the patient will be graded according to CTC 4.0 and via pill counts of anti-diarrheal medication measured each cycle.

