We will use descriptive statistics to summarize the total scores for the Osoba Module, used to measure the effect of nausea and vomiting on quality of life, for each treatment group by cycle of therapy. We will compare the treatment groups with respect to the Osoba Module score with a Mann-Whitney test. We will also tabulate the responses to each of the 5 questions of the Osoba Module for each treatment group. We will also use repeated measures analysis of variance methods to model the effect of nausea and vomiting on quality of life over all cycles of therapy.

We will use descriptive statistics to summarize the number and amount of dose reductions for each treatment group for each cycle of therapy. We will also use repeated measures analysis of variance methods to model the number and amount of dose reductions over all cycles of therapy. We will similarly analyze the number and doses of rescue medications and the amount of diarrhea experienced over the course of therapy.

Technical Details

We assume a beta (1.1, 2.9) prior distribution for the treatment failure rate for each treatment. This prior distribution has a mean of 0.275 and a standard deviation of 0.200. As the trial progresses these prior distributions will be updated with the data that have accrued.

Let F_{OO} and F_{GP} be the treatment failure rates for treatments “Oral Ondansetron” (OO) and “Granisetron Patch” (GP), respectively. Prior to enrolling the 40th and subsequent patients we will calculate the randomization probability as follows. We will first calculate $\pi_{GP}(\text{data}) = \Pr(F_{GP} < F_{OO} \mid \text{data})$ and $\pi_{OO}(\text{data}) = 1 - \pi_{GP}(\text{data})$. The randomization probability for GP will then be defined as $r_{GP} = \frac{\sqrt{\pi_{GP}}}{\sqrt{\pi_{GP}} + \sqrt{\pi_{OO}}}$, and the randomization probability for OO will be $r_{OO} = 1 - r_{GP}$.

Accrual to treatment arm OO will be suspended if $\Pr(F_{OO} < 0.225 \mid \text{data}) < 0.10$. Similarly, accrual to treatment arm GP will be suspended if $\Pr(F_{GP} < 0.225 \mid \text{data}) < 0.10$. If at any point during the trial $\pi_{GP}(\text{data}) > 0.925$ (< 0.075) the trial will be terminated and treatment “Granisetron Patch” will be selected as superior (inferior). If the maximum number of patients is enrolled in the trial and $\pi_{GP}(\text{data}) > 0.915$ (< 0.085) treatment “Granisetron Patch” will be selected as superior (inferior).

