7.6 OBTAINING ADVERSE EVENT INFORMATION

At every study visit, patients will be asked a standard non-leading question to obtain any medically related changes in their well-being. In addition to patient or Investigator observations, AEs will be documented from any data collected (e.g., laboratory values, physical examination findings), or other documents that are relevant to patient safety.

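### The exploratory diarrhea endpoint has no planned constipation counterpart: constipation is captured only as an unsolicited adverse event and is not compared by arm

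*Combined protocol and SAP*

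**What the plan says.** Section 1.3.1 gives the mechanism, that "5HT3 blockers tend to cause constipation as a medication side effect", and from it predicts that women "receiving the continuous administration of a 5HT3 blocker via the patch (Sancuso) will have less diarrhea than those receiving only 72 hours" of scheduled oral drug.

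Section 2.0 reports from an earlier randomized comparison: "Constipation was the more common side effect in the patch group (6.6% of patients compared to 3.1% in the oral group". It introduces the two background studies with the words "Two studies have evaluated transdermal vs oral granisetron".

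Section 4.3 makes the weekly amount of diarrhea the only exploratory endpoint; it "will be graded according to CTC 4.0 and via pill counts of anti-diarrheal medication measured each cycle". Section 4.1 provides a diary for anti-diarrheal drugs. Section 5.0 adds: "We will similarly analyze the number and doses of rescue medications and the amount of diarrhea experienced over the course of therapy". The sentences just before it describe descriptive statistics by group and cycle and repeated measures analysis of variance.

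Constipation is not an endpoint. It is the first item in the section 7.2 list of common adverse events. Under section 4.1, "Adverse event monitoring and concomitant medications will be recorded prior to each cycle and one week after the last cycle". Section 7.1 grades adverse events by CTCAE v4.0, and section 7.8 asks that changes in severity be documented. On elicitation, section 7.6 says that "patients will be asked a standard non-leading question". Section 5.0 contains no adverse event analysis by arm.

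**The concern.** The argument for less diarrhea on the patch is also an argument for more constipation on it. The plan makes an endpoint of the favorable side only.

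This affects what the diarrhea result can mean. A lower average diarrhea grade on the patch could come from women moving from diarrhea to normal bowel function, or from women moving past normal into constipation. The anti-diarrheal pill count falls in both cases. Neither measure separates the two, and no planned analysis sets constipation beside them. A report that followed section 5.0 to the letter could present less diarrhea on the patch without the table a reader needs to judge it.

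**Working it through.** **1. The two effects side by side**

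| | Diarrhea | Constipation |
|---|---|---|
| Status | Exploratory endpoint (4.3) | Listed common adverse event (7.2) |
| Grade | CTC 4.0, required weekly (4.3) | CTCAE v4.0, when reported (7.1) |
| Elicitation | A grade is due each week | General non-leading question (7.6) |
| Timing | Each cycle | Before each cycle and one week after the last (4.1) |
| Drug use | Diary and pill count (4.1, 4.3) | Concomitant medication record (4.1); no diary |
| By-arm analysis | Descriptive by cycle, plus repeated measures (5.0) | None |

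Section 7.5 adds that a condition present at screening which does not worsen is not reported as an adverse event. The adverse event record is therefore not a weekly bowel-status measure.

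**2. What a diarrhea grade does with constipation**

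| Change in a patient | Change in diarrhea grade |
|---|---|
| Normal to grade 2 constipation | 0 to 0: no change |
| Grade 2 diarrhea to normal | 2 to 0: improved |
| Grade 2 diarrhea to grade 2 constipation | 2 to 0: improved |

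The first row cannot be told from a patient with no bowel problem, and the third cannot be told from the second.

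**3. Why the plan's own reasoning predicts a difference**

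The patch delivers drug for all 7 days of the week, 7 × 24 = 168 hours. The scheduled oral drug covers 72 hours after infusion. That is the contrast in section 1.3.1, and it does not depend on any background rate.

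**4. How much a constipation comparison could show**

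The documents derive no figure from the constipation rates, so there is none to reproduce. The following is an illustration. Inputs: 6.6% and 3.1% (section 2.0), with the oral granisetron rate standing in for ondansetron; arm sizes from the enrollment limits of 75 and 150 split equally, and from Table 1. Two-sided 5% is my assumption.

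- Expected cases = n × rate.
- 95% half-width = 1.96 × √(p₁(1−p₁)/n₁ + p₂(1−p₂)/n₂).
- Power = Φ((|p₂−p₁| − 1.96 × SE₀)/SE₁), with SE₀ from the pooled rate and SE₁ from the separate rates.

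| Oral / patch n | Expected cases | Half-width | Power |
|---|---|---|---|
| 37.5 / 37.5 (N = 75) | 1.2 / 2.5 | 9.7 points | 10% |
| 35.4 / 61.9 (Table 1, 0.2750 vs 0.1375) | 1.1 / 4.1 | 8.4 points | 9% |
| 48.9 / 49.2 (Table 1, both 0.2750) | 1.5 / 3.2 | 8.5 points | 12% |
| 75 / 75 (N = 150) | 2.3 / 5.0 | 6.9 points | 17% |

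Example, row 2: 35.4 × 0.031 = 1.1 and 61.9 × 0.066 = 4.1. SE₁ = √(0.031 × 0.969/35.4 + 0.066 × 0.934/61.9) = 0.043, and 1.96 × 0.043 = 0.084.

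For 80% power at these rates the trial would need about 591 patients per arm. From a 3.1% oral rate, the patch rate detectable with 80% power is about 25% at N = 75 and 17% at N = 150.

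**The case against.** The strongest reply is that constipation is already covered. It is listed first among the common events, recorded before every weekly cycle, graded on the same scale as diarrhea, and followed for change in severity. Laxatives would appear among the concomitant medications, and section 7.5 records any treatment an event requires. This stands against two stronger readings. A reader might infer that constipation has no graded weekly record, or that a shift into constipation would be reported only as benefit. Neither is supported, because section 7.1 makes the investigator responsible for reporting all adverse events. What differs is that constipation is unsolicited and that no by-arm comparison is planned.

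A reader might also take 6.6% against 3.1% as the difference to expect here, or compound it over five weekly cycles. The documents support neither. The comparator was oral granisetron, and section 1.3.1 attributes constipation to the drug class, hence to both arms. The rates are per patient, and nothing suggests an independent risk each week. Nor can one say that unsolicited reporting would push counts below those rates, since section 2.0 does not say how they were collected.

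A third reply is that a comparison would be too imprecise to help. That rules out a powered test and makes cycle-by-cycle contrasts nearly empty. It does not rule out an overall descriptive table: diarrhea is itself exploratory and still has a planned analysis.

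Finally, the diarrhea endpoint enters neither the superiority rule nor the adaptive randomization, which use late-phase treatment failure only. That is correct, and it limits the point to the exploratory objective and the safety summary.

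**Conclusion.** The point holds as an asymmetry in measurement and analysis. Diarrhea has a required weekly grade, a pill count and a by-arm model. Constipation, which the plan's own mechanism predicts, has an unsolicited adverse event record and no planned comparison. As planned, the diarrhea result cannot distinguish better bowel function from a shift into constipation.

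The conclusion rests on the text of sections 1.3.1, 4.1, 4.3, 5.0 and 7.1 to 7.8, and on no assumed rate. The size of any constipation excess over ondansetron cannot be estimated from the documents. The 9% to 17% power range depends on the borrowed rates and an assumed two-sided 5% level, and serves only to show that the added result should be descriptive. The primary comparison is unaffected. The change is worth making because it alters what the diarrhea endpoint can mean, at little cost.

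**What to change.** - **Section 4.3 and the weekly assessment:** grade constipation by CTC 4.0 alongside diarrhea, each week and in both arms, with a value recorded even when there is none.
- **Laxative use:** extract it from the concomitant medication record already taken before each cycle. No new diary is needed.
- **Section 5.0:** tabulate worst constipation grade by arm beside worst diarrhea grade, with the between-arm difference and a 95% interval. State that this is descriptive and not a powered test.

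The cost is one assessment item and one table, with no extra visits. The downside is that a directed question will raise reported constipation. The increase may be unequal between arms, because the documents describe no blinding of patch against tablet. The diarrhea item already carries that limitation, and the report should state it for both.
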